5.7 Packaging

HORIZANT ER 600mg tablets will be overencapsulated by the CCF IDS pharmacy. A matching placebo capsule will be compounded by the pharmacy to match that of the active study drug. Both will be packaged in vials containing ten capsules each, and will be dispensed accordingly to RedCap randomization (10 tablets per bottle).

5.8 Blinding of Study Drug

Principal Investigator and research fellow primarily involved in the study and follow-ups will be blinded to the treatment assignment. The study personnel listed above will not know or discuss the treatment assignment, medical history or status of any subject. Randomization will occur independently. Clinical evaluators for the outcomes will be blinded to group allocation and clinical research fellows not involved in evaluations will prepare the study drug/packet. Clinicians including nurses will be blinded to monitoring and will be required to perform their standard of care management after surgery.

5.9 Receiving, Storage, Dispensing and Return

5.9.1 Receipt of Drug Supplies

Cleveland Clinic Fairview hospital and Cleveland Clinic Main Campus will maintain accurate records of the receipt of the drug and will inform the sponsor and the principal investigator after the drug is received. Upon receipt of the study treatment supplies, an inventory must be performed and a drug receipt log filled out and signed by the person accepting the shipment. It is important that the designated study staff counts and verifies that the shipment contains all the items noted in the shipment inventory. Any damaged or unusable study drug in a given shipment will be documented in the study files. The

investigator must notify study sponsor of any damaged or unusable study treatments that were supplied to the investigator's site.

5.9.2 Storage

The study drug will be stored by the pharmacy on the shelf at room temperature. No special handling requirements during storage.

5.9.3 Dispensing of Study Drug

Cleveland Clinic Fairview hospital and Cleveland Clinic Main Campus will maintain accurate records demonstrating dates and amount of study drug received, to whom they are dispensed (subject-by-subject accounting), and accounts of any study drug accidentally or deliberately destroyed.

Study drug reconciliation will be performed to document drug assigned, drug consumed, and drug remaining. This reconciliation will be logged on the reconciliation form, and signed and dated by the study team.

5.9.4 Return or Destruction of Study Drug

The investigator will return all unused vials of study drug to Xenoport Inc. pursuant to instructions (unless agreed otherwise by Xenoport Inc.). At the completion of the study, there will be a final reconciliation of drug shipped, drug consumed, and drug remaining. This reconciliation will be logged on the drug reconciliation form, signed and dated. Return or destruction of study drug will be done per Cleveland Clinic Fairview and Cleveland Clinic Main Campus pharmacy protocol.

6. STUDY PROCEDURES

6.1 Pre-registration and Screening

Medical history involves a detailed history of present illness. Any significant past medical or surgical history will be noted. Patient will be asked for any allergies to gabapentin or gabapentinoids (Neurontin, Lyrica, Gralise or Horizant).

Pre-op evaluation will be checking laboratory values through EPIC (electronic privacy information center). Available preoperative laboratory tests and medication list will be recorded. Renal function tests will not be ordered exclusively for study purposes. Only pre-ordered renal function tests by the primary doctor will be used to screen patients. Only patients within the approved creatinine range (≤ 1.50 mg/dl) will be enrolled.

6.2 Visit 1 (Day of Surgery)

Patients will be given GEn 600 mg single dose with sips of water 2 hours before surgery and then restarted within 6 hours of completion of surgery. GEn will be administered to the patient 600 mg bid for three post-operative days with meals.

Physical evaluations include monitoring vital signs, checking general well-being and pain evaluation both pre-operatively and post-operatively. Patients will be evaluated by orthopedic

surgeons pre-operatively and post-operatively as per their protocol. Physical therapy will evaluate the patients for pain, mobility and strength as per physical therapy protocol. Physical therapy and orthopedic surgeons will record and document their findings in EPIC.

Patients will be monitored throughout their stay in the hospital and will be asked to report any adverse event or any untoward event to the research fellow. Patients will be also be inquired for any side effects during the phone call made 3 months after surgery.

Patient discharged prior to 72 hours will be followed-up via phone call(s). Phone call followup will be performed once a day till 72 hours.

6.3 Visit 2 (Phone call).

Patients will be contacted by telephone at 3 months after surgery and queried regarding presence of new pain since surgery and its interference with activities of daily living. Phone call is made with the purpose of checking for pain conversion from acute to chronic and to check for any adverse event.

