3. STUDY DESIGN

3.1 General Design

A randomized controlled trial to determine the effect of gabapentin enacarbil on opioid consumption and pain scores in patients having primary hip or knee replacement surgery with spinal anesthesia. Randomization will be web-based and stratified by type of surgery. Allocation will be concealed until shortly before drug/placebo administration.

Participating patients will be randomly assigned to standard management with GEN or to standard management with placebo. Patients will be given GEN 600 mg bid or placebo 600 mg bid for 1 preoperative day and will receive 600 mg GEN or placebo about 2 hours before surgery and then restarted on GEN or placebo 600 mg within 6 hours of surgery, and then 600 mg bid for three additional days.

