5.2 Treatment Regimen

Gabapentin enacarbil 600 mg or placebo will be administered orally one day pre-operatively 12 hours apart with meals and 600 mg gabapentin enacarbil or placebo dose 2 hours before the surgery with sips of water. Post-operative dose of 600 mg gabapentin enacarbil or placebo should be resumed within 6 hours of completion of procedure with sips of water. Patient will receive 600 mg gabapentin enacarbil or placebo doses three additional days postoperatively 12 hours apart with meals.

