5.6 Prior and Concomitant Therapy

Patient will not receive any gabapentinoids from the start of study drug to the end of postoperative 72 hours period. All other pain medications will be allowed.

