6.4 Study Calendar of Procedures

	Pre-operative clinical evaluation visit (Outpatient)	Treatment Phase (Inpatient)						Follow Up (Phone call)
	Baseline/ Enrollment 1-2 weeks before surgery	2 Days prior to Surgery	1 Day Prior to Surgery (-1)	Day of Surgery (Day 0)	POD 1	POD 2	POD 3	3 Months after surgery
Screening visit ¹	X							
Randomization/ Enrollment	X							
Medical History ² / Disease History Pre-op Evaluation ³	X			X				
GEn PO dose ⁴ /Placebo			X	X	X	X	X	
Vital Signs	X		X	X	X	X	X	
Physician Evaluation ⁵	X			X	X	X	X	
Monitoring and recording adverse events ⁶			X	X	X	X	X	X
Data acquisition ⁷	X		X	X	X	X	X	X
Phone call		X ⁸				X ¹⁰	X ¹⁰	X ⁹

Footnotes:

¹ Screening visit would be within a month before surgery at the pre-operative clinical evaluation visit. Patients will be screened using inclusion and exclusion criteria. The study will be explained to the patients in detail. The side effects of GEn will be explained and patients will be consented for the study during this time. After eligibility is confirmed, patients will receive complete information about the study both verbally and in writing. Informed consent will be obtained from the patients prior to randomization and study-specific procedures.

² Medical histories involve a detailed history of present illness. Any significant past medical or surgical history will be noted. Patient will be asked for any allergies to gabapentin or gabapentinoids (Neurontin, Lyrica, Gralise and Horizant).

³ Pre-op evaluations will be checking laboratory values through EPIC (electronic privacy information center). Available preoperative laboratory tests and medication list will be recorded. Renal function tests will be not be ordered exclusively for study purposes. Only pre-ordered renal

function tests by the primary doctor will be used to screen patients. Only patients within the approved creatinine range (≤ 1.50 mg/dl) will be enrolled.

⁴ Patients will be administered GEn 600 mg bid PO dose. Patient will be asked to take GEn 600 mg bid one day prior to surgery with meals. Patients will be given GEn 600 mg single dose with sips of water 2 hours before surgery and then restarted within 6 hours of completion of surgery. GEn will be administered to the patient 600 mg bid for three post-operative days with meals.

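### The ban on other gabapentinoids (section 5.6) ends at 72 hours, but the last study capsule is due at about 72-78 hours and peaks later still (minor)

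*Combined protocol and SAP*

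**What the plan says.** **Restriction.** Section 5.6 states: "Patient will not receive any gabapentinoids from the start of study drug to the end of postoperative 72 hours period". The next sentence is permissive: "All other pain medications will be allowed".

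**Dosing.** Section 3.1 has patients "then restarted on GEN or placebo 600 mg within 6 hours of surgery, and then 600 mg bid for three additional days". Section 5.2 agrees. For the restart it says "Post-operative dose of 600 mg gabapentin enacarbil or placebo should be resumed within 6 hours of completion of procedure with sips of water", and for the remaining capsules "Patient will receive 600 mg gabapentin enacarbil or placebo doses three additional days postoperatively 12 hours apart with meals". Section 5.7 fixes the supply: "Both will be packaged in vials containing ten capsules each".

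**Contact after discharge.** For patients who leave before 72 hours, section 6.2 says "Phone call followup will be performed once a day till 72 hours". The calendar in section 6.4 marks a call for such patients on POD 2 and POD 3. Its row "Monitoring and recording adverse events" is marked through POD 3 and then at 3 months. Nothing in the document extends the restriction or the calls to the last capsule.

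**The concern.** A ban on same-class drugs that begins with study drug would be expected to last as long as study drug does. Here it is tied to the 72-hour mark, which on the stated spacing comes no later than the last capsule and up to 6 hours before it. In that interval, and while the capsule is being absorbed, the text lets a clinician who does not know the allocation start another gabapentinoid. Section 1.2 lists sedation and dizziness among the side effects, and opioids may be in use at the same time because other analgesics are unrestricted. What is at stake is a small, avoidable safety exposure around one capsule. The calls raise a lesser, related matter: a patient who takes the last capsule at home may have no scheduled contact after it until the 3-month call.

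**Working it through.** **Inputs from the protocol.** Two capsules on the day before surgery, one about 2 hours before surgery, a restart 0-6 hours after surgery, then two a day for three days at 12-hour spacing (3.1, 5.2). Ten capsules per vial (5.7). Tmax 5.0 h fasted and 7.3 h fed (1.4). Half-life 4.8-8.7 h (1.2, stated for gabapentin, not for the prodrug). Restriction and calls end at 72 h (5.6, 6.2).

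**Assumptions, not in the protocol.** Surgery ends between 08:00 and 20:00; the POD 3 evening capsule is taken between 18:00 and 20:00; a POD 3 call is made between 08:00 and 17:00.

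1. **Capsule count.** 2 + 1 + 1 + (3 × 2) = 10. This reproduces the ten-capsule vial, so the schedule is read correctly. Seven of the ten are postoperative.

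2. **Last capsule, 12-hour spacing.** Restart time + 6 × 12 h = (0 to 6) + 72 = 72 to 78 h. No clock-time assumption is needed.

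3. **Last capsule, calendar days.** 72 h + (clock time of the POD 3 evening capsule − clock time at the end of surgery). Earliest: 72 + 18 − 20 = 70 h. Latest: 72 + 20 − 8 = 84 h. It falls before 72 h only if surgery ends later in the day than the capsule is taken, so after 18:00 at the earliest.

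4. **Peak of the last capsule** (capsule time + Tmax).
   - 12-hour spacing: 72 + 5.0 = 77 h to 78 + 7.3 = 85.3 h, which is 5 to 13.3 h past the end of the ban.
   - Calendar days: 70 + 5.0 = 75 h to 84 + 7.3 = 91.3 h, which is 3 to 19.3 h past it.
   - With an 18:00 capsule, even a fasted peak by 72 h would need surgery to end at 23:00 or later.

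5. **Is exposure higher after the last capsule?** At 12-hour dosing, the share of steady state reached at the nth postoperative capsule is 1 − 2^(−12n/t), ignoring the preoperative capsules.
   - t = 8.7 h: 0.9916 at n = 5 (the POD 2 evening capsule) and 0.9988 at n = 7 (the last), a rise of 0.7%.
   - t = 4.8 h: 0.9998 at n = 5, with a rise of 0.02% by n = 7.

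   The last capsule adds practically nothing to the level already reached on POD 2.

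6. **Is one day after the last capsule a sensible margin?** Share of peak left at 24 h = 2^(−(24 − Tmax)/t). Lowest: 2^(−19.0/4.8) = 0.064. Highest: 2^(−16.7/8.7) = 0.264. So about 6-26% remains.

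7. **Added length of the restriction.** Last capsule + 24 h is 96-102 h (12-hour spacing) or 94-108 h (calendar), that is, 24-30 h or 22-36 h beyond 72 h.

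8. **The POD 3 call.**
   - If the last capsule is taken at 18:00-20:00, its fed peak is at 01:18-03:18 on POD 4. A call at 08:00-17:00 comes 1 to 12 h before the capsule (18 − 17; 20 − 8).
   - On strict 12-hour spacing the order can reverse. If surgery ends at 08:00 and the restart is immediate, the last capsule is at 08:00 on POD 3 and peaks at 13:00-15:18, so a 17:00 call would follow the peak.
   - From 72 h to the 3-month call is 90 − 3 = 87 days.

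**The case against.** **The 72-hour limit is deliberate.** It is the protocol's outcome horizon: opioid use, nausea and vomiting, pain scores and QoR-15 all stop there or at discharge. A ban ending with the outcomes protects the endpoints, and no rule in the document says it must follow the last capsule. This explains the choice and stands as such. It does not remove the overlap.

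**The overlap is improbable.** Section 4.2 excludes anyone who used a gabapentinoid within one month, so it would take a new prescription within hours of the 72-hour mark. The document gives no sign that this is common. This also stands, and it limits the size of the point.

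**The 70-84 hour range rests on assumed clock times.** Correct. The range from the stated spacing is 72-78 h, and at its lower end the last capsule coincides with the end of the ban. The conclusion uses only the peak after 72 h, which holds on both readings.

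**Stronger readings.** A reader might infer that adverse events after the last capsule go uncaptured. The document does not support that. POD 1-3 is planned as inpatient, the calendar marks adverse-event monitoring and a call on POD 3, and that call can fall after the last capsule. Patients are asked to report events, section 8.2 requires all events in the study period to be recorded, and the 3-month call asks about side effects. Nor does the protocol say what the daily calls cover, so treating them as a safety window is an inference. A reader might also infer a bias in the efficacy comparison. There is none, because the primary outcomes end at 72 hours or discharge, no later than the ban.

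**Conclusion.** The point holds as a minor mismatch in section 5.6. The ban on other gabapentinoids ends at 72 h, the tenth capsule is due at 72-78 h on the stated spacing, and its peak is 5 to 13.3 h past the end of the ban (3 to 19.3 h on the assumed clock times). The peak result rests on the Tmax values in section 1.4. The exposure result also assumes that the gabapentin half-life in section 1.2 applies to the prodrug.

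The practical size is small: one capsule of ten, at a level under 1% above that of capsules already monitored, and an overlap that needs a new prescription. The timing of the calls is a lesser matter that justifies an optional addition. It concerns only patients who are at home when the last capsule is due, and the protocol gives no figure for how many that will be.

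**What to change.** **Main change.** Reword section 5.6 so that the restriction runs from the first study capsule through the last one plus about one day, with the margin set by the clinical team. It should in no case end before 72 h, so that a patient who stops study drug early stays covered for the outcome window. The cost is one sentence and a co-medication restriction about 24-30 h longer (22-36 h on the assumed clock times), which should affect few patients because recent users are already excluded.

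**Optional addition.** For every patient discharged before the last capsule is due, keep the POD 3 call and add one short call on about POD 4. It should ask whether the last capsule was taken and about the side effects named in section 1.2, and it should be marked in the section 6.4 calendar.
- Offer it to all such patients. If it went only to those known to have taken the capsule, it could not show who missed it, and so would not help the compliance monitoring in section 5.5. Drug reconciliation (5.9.3) remains a second source.
- Add it rather than moving the POD 3 call, which is the scheduled contact nearest the end of the 72-hour outcome window.

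The cost is one extra brief call per early-discharged patient by staff who already make such calls. Neither change touches the outcomes, the analysis or the sample size.

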6.4 Study Calendar of Procedures

	Pre-operative clinical evaluation visit (Outpatient)	Treatment Phase (Inpatient)						Follow Up (Phone call)
	Baseline/ Enrollment 1-2 weeks before surgery	2 Days prior to Surgery	1 Day Prior to Surgery (-1)	Day of Surgery (Day 0)	POD 1	POD 2	POD 3	3 Months after surgery
Screening visit ¹	X							
Randomization/ Enrollment	X							
Medical History ² / Disease History Pre-op Evaluation ³	X			X				
GEn PO dose ⁴ /Placebo			X	X	X	X	X	
Vital Signs	X		X	X	X	X	X	
Physician Evaluation ⁵	X			X	X	X	X	
Monitoring and recording adverse events ⁶			X	X	X	X	X	X
Data acquisition ⁷	X		X	X	X	X	X	X
Phone call		X ⁸				X ¹⁰	X ¹⁰	X ⁹

Footnotes:

¹ Screening visit would be within a month before surgery at the pre-operative clinical evaluation visit. Patients will be screened using inclusion and exclusion criteria. The study will be explained to the patients in detail. The side effects of GEn will be explained and patients will be consented for the study during this time. After eligibility is confirmed, patients will receive complete information about the study both verbally and in writing. Informed consent will be obtained from the patients prior to randomization and study-specific procedures.

² Medical histories involve a detailed history of present illness. Any significant past medical or surgical history will be noted. Patient will be asked for any allergies to gabapentin or gabapentinoids (Neurontin, Lyrica, Gralise and Horizant).

³ Pre-op evaluations will be checking laboratory values through EPIC (electronic privacy information center). Available preoperative laboratory tests and medication list will be recorded. Renal function tests will be not be ordered exclusively for study purposes. Only pre-ordered renal

function tests by the primary doctor will be used to screen patients. Only patients within the approved creatinine range (≤ 1.50 mg/dl) will be enrolled.

⁴ Patients will be administered GEn 600 mg bid PO dose. Patient will be asked to take GEn 600 mg bid one day prior to surgery with meals. Patients will be given GEn 600 mg single dose with sips of water 2 hours before surgery and then restarted within 6 hours of completion of surgery. GEn will be administered to the patient 600 mg bid for three post-operative days with meals.

⁵ Physical evaluations include monitoring vital signs, checking general wellbeing and pain evaluation both pre-operatively and post-operatively. Patients will be evaluated by orthopedic surgeons pre-operatively and post-operatively as per their protocol. Physical therapy will evaluate the patients for pain, mobility and strength as per physical therapy protocol. Physical therapy and orthopedic surgeons will record and document their findings in EPIC.

⁶ Patients will be monitored throughout their stay in the hospital and will be asked to report any adverse event or any untoward event to the research fellow. Patients will be also be inquired for any side effects during the phone call made 3 months after surgery.

⁷ Data will be collected through personal interview and through electronic medical records. Data will also be collected through the phone call made 3 months after surgery.

Pre-operative data collection:

1. Pain scores using numerical rating scores (NRS) during the pre-operative evaluation visit
2. Brief pain inventory (BPI) at pre-operative evaluation visit.
3. Demographic data to be obtained includes height (cm), weight (kg), age (yr.), gender, (ASA) physical status, and self-declared ethnicity.
4. Patients will be questioned for social history (tobacco) and medical history (pulmonary disease, kidney disease, diabetes mellitus, neurological disease, chronic pain conditions, illegal drug usage, alcohol abuse, myocardial infarction, previous surgery or stent placement and medications usage).
5. Available preoperative laboratory tests and medication list will be recorded.
6. Individual risk for nausea and vomiting will be determined using the Apfel score.

Post-operative data collection:

1. Pain scores using numerical rating scores (NRS):
 - a. Every 15 minutes for the first hour after surgery.
 - b. Every four hours after the first hour until 72 hours after the surgery.
2. Brief pain inventory (BPI) prior to hospital discharge or at 72 hours post op whichever comes first
3. The QoR-15 score to formally evaluate quality of recovery. The QoR-15 score is a validated scoring system allows quantification of patient's early postoperative health status, which is also a description of quality of recovery. The QoR-15 scoring will be done prior to hospital discharge or at 72 hours post op whichever comes first.
4. Data obtained from electronic medical records will include: operation time, surgery type, intraoperative opioid consumption, postoperative opioid consumption in PACU and in ward, breakthrough pain medication requirements, pain scores in PACU and ward, requirement of antiemetics for nausea and vomiting, requirement of antihistaminic medications, requirement of laxatives for constipation, ambulation time, flatus, ileus, bowel movements, length of stay and any side effects or complications. Preoperative and postoperative laboratory data including but not limited to renal function will also be collected from electronic medical records. Patient functionality will also be recorded including, bathing, toileting, walking and

moving.

⁸ Phone calls will be made purely to remind patients to take their pre-operative medication.

⁹ Phone calls will be made to check for any adverse event and with the intention to assess chronic pain.

¹⁰ Phone call made for follow-up if the patient is discharge prior to 72 hours.

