5.3 Method for Assigning Subjects to Treatment Regimen

Participating patients will be randomly assigned to gabapentin enacarbil or placebo. Randomization will be web-based through REDCap and stratified by type of surgery. Allocation will be concealed until shortly before drug/placebo administration. Randomization will be stratified by type of surgery (hip versus knee). Randomization codes will be web based using random-sized blocks, and treatment assignment (gabapentin enacarbil or placebo) will be done using a password-protected website administered by the Department of Outcomes Research statistical team at Cleveland Clinic.

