7. STATISTICAL PLAN

7.1 Sample Size Determination

Sample size is fixed to be at 100 patients. We will recruit 100 patients having hip or knee arthroplasties with spinal anesthesia. 50 patients control will be given the placebo for five days and 50 patients will be given GEn 600 mg bid for five days.

Power consideration. Sample size is fixed to be at 100 patients. Power estimation is based on the analysis of superiority on opioid consumption because this analysis requires more patients than the superiority analysis on pain scores. As it is stated in the hypothesis to claim positive effect of gabapentin enacarbil at least on one of these outcomes should be superior. Assuming the pilot study recruited total 100 patients and coefficient of variation (SD/mean) of 0.7 for both groups, we would have about 90% power to detect the ratio of 0.63 in geometric means in opioid consumption (i.e., a geometric mean opioid consumption decreases more than 37% in gabapentin enacarbil patients) comparing gabapentin enacarbil patients to patients receiving placebo at significance level of 0.0125.

If the assumptions appear to be too optimistic and study turns out to be underpowered, nevertheless treatment effects and variability identified in this pilot investigation can be used to plan a future study with sufficient power.

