7.2 Statistical Methods

The modified intention-to-treat approach will be utilized: patients who were randomized, had the procedure and received any amount of treatment will be included in the analysis. The per-protocol analysis (on patients who were randomized, had the procedure and followed the treatment regimen at least 50% of the times) will be conducted for the primary outcome as a sensitivity analysis.

First, randomized groups will be compared for balance on potentially confounding baseline demographic and preoperative variables using descriptive statistics.

Primary outcome. In the primary hypothesis, quality of postoperative analgesia will be characterized using both pain scores and total postoperative opioid consumption within 72 hours of the surgery or till discharge. We will consider gabapentin enacarbil group better than placebo group on the postoperative pain management if gabapentin enacarbil group is found noninferior (i.e., not worse) on both outcomes and superior on at least one of the outcomes. We define the a-priori noninferiority pain score delta as 1 point and the opioid delta as 1.1 for the ratio in geometric

means IV morphine equivalent doses (meaning 10% difference between group's median doses). Thus, our primary hypothesis will be assessed in a joint hypothesis-testing framework described by Mascha and Turan (42).

We will first estimate confidence intervals for the treatment effect for both pain score and opioid consumption. Assuming lognormal distribution of opioid consumption, we will evaluate the percent difference in geometric mean IV morphine equivalent dose between the two groups using a log-linear regression model. To evaluate the difference in mean pain scores we will first summarize the pain scores by computing time weighted average (TWA) pain score for each patient. Then we will use a linear regression model to assess the treatment effect on the TWA pain scores.

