Our joint hypothesis testing will consist of two steps. First, we will evaluate the noninferiority of gabapentin enacarbil to placebo group on both outcomes. Noninferiority (being “not worse”) of gabapentin enacarbil group will be concluded for both outcomes at the significance level of 0.025 if the upper limit of 95% confidence interval is below the corresponding noninferiority delta. Second, if noninferiority is concluded for both pain scores and opioid consumption, we will proceed to a 1-tailed superiority test on each outcome in the same direction as the noninferiority testing. Superiority testing will be done at the overall 0.025 significance level and will be adjusted for multiple testing (two outcomes) via Bonferroni correction ($0.025/2=0.0125$); superiority will thus be claimed for a particular outcome if the 97.5% confidence interval is below zero (below one for ratio in geometric means for opioid). Overall Type I error rate for the joint hypothesis testing will be maintained at 0.025 (we choose 0.025 instead of 0.05 because we have to consider treatment effect both directions gabapentin enacarbil vs. placebo and placebo vs. gabapentin enacarbil) even though both noninferiority and superiority will be tested at the 0.025 level. This is because noninferiority on both outcomes and superiority on at least one is required to claim gabapentin enacarbil group better than placebo group, and thus the joint hypothesis framework is an intersection-union test (which does not require additional adjustment for testing two sets of hypotheses).

In addition to the confidence intervals, tests giving the P-values for noninferiority and superiority will be performed. For noninferiority, two 1-tailed t-tests for each outcomes will be done to assess whether the difference in means pain scores (or ratio in geometric means for opioid) is below the given delta (log of given delta for opioid). For superiority, two 1-tailed t-tests will be done in the same direction as the noninferiority testing to assess whether the difference in means pain scores (or ratio in geometric means for opioid) is below zero (one). Estimates of treatment effect and standard error will be based on the regression models described above. .

Secondary outcomes. We will compare two randomized groups on each secondary outcome using appropriate 2-tailed tests for superiority: t-tests or Wilcoxon rank sum tests for continuous outcomes as of duration of hospitalization and QoR-15 satisfaction score.

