To assess if administration of gabapentin enacarbil decreases the incidence of nausea and vomiting within initial 72 hours of the surgery and the risk of pain conversion from acute to chronic chi-square tests will be used.

The significance level for the set of secondary outcomes will be preserved at 0.05 overall by using a criterion of $P < 0.05/4 = 0.0125$ for each test (applying a Bonferroni correction for multiple testing of the 4 secondary outcomes).

R statistical software version 2.12.1 (The R Foundation for Statistical Computing, Vienna, Austria)

and SAS statistical software version 9.3 (SAS Institute, Cary, NC, USA) for 64-bit Microsoft Windows will be used for all statistical analysis.

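### The Apfel score is collected as the measure of nausea and vomiting risk, but the planned chi-square for 72-hour nausea and vomiting does not use it: a small, optional gain in precision is forgone

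*Combined protocol and SAP*

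**What the plan says.** - **Score collected.** Section 6.4, footnote 7, item 6 of the pre-operative data: "Individual risk for nausea and vomiting will be determined using the Apfel score".
- **Test.** Section 7.2, secondary outcomes, names the method for the "incidence of nausea and vomiting within initial 72 hours of the surgery and the risk of pain conversion from acute to chronic chi-square tests". No covariate or stratum is mentioned.
- **Level and sidedness.** Section 7.2: "We will compare two randomized groups on each secondary outcome using appropriate 2-tailed tests for superiority", and "using a criterion of $P < 0.05/4 = 0.0125$ for each test".
- **Randomization.** Section 5.3: "Randomization will be stratified by type of surgery (hip versus knee"). The Apfel score is not a stratification factor.
- **Baseline variables.** Section 7.2: "randomized groups will be compared for balance on potentially confounding baseline demographic and preoperative variables using descriptive statistics". The Apfel score is not named. It could fall under this wording, but the check is descriptive and leaves the test unchanged.
- **Size.** Section 7.1: "50 patients control will be given the placebo for five days and 50 patients will be given GEn 600 mg bid for five days".

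**The concern.** The plan records a baseline variable that grades risk of the Secondary Aim 2 outcome, then tests that outcome without it. Two things are at stake.

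The first is precision. Conditioning on a baseline variable that predicts a binary outcome usually gives a somewhat more powerful test of treatment. This endpoint has 50 patients per arm and a level of 0.0125, so it has little power to spare.

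The second is prespecification. Neither the randomization nor the analysis controls baseline nausea and vomiting risk. If the balance check shows that one arm drew higher-risk patients, the plan offers no response, and an adjustment chosen at that point would be post hoc.

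**Working it through.** **1. The plan's own figures.** The level reproduces: 0.05/4 = 0.0125. The plan gives no power for nausea and vomiting. The only stated power is about 90% for opioid consumption. With SD of the log = sqrt(ln(1 + 0.7²)) = 0.631, difference = |ln 0.63| = 0.462, 50 per arm and one-sided 0.0125, a noncentral t calculation gives 91.5%, in line with the statement.

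**2. What the chi-square can detect.** Event rates are assumed, because the documents give none. For 40% versus 20%:
- pooled rate 0.30; null SE = sqrt(2 × 0.30 × 0.70/50) = 0.0917
- alternative SE = sqrt((0.40 × 0.60 + 0.20 × 0.80)/50) = 0.0894
- critical z (two-sided 0.0125) = 2.498
- power = Φ((0.20 − 2.498 × 0.0917)/0.0894) = Φ(−0.32) = 37%

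The same formula gives 53% for 50% versus 25%, and 71% for 60% versus 30%. For 80% power, a 40% control rate would have to fall to about 11%.

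**3. Validity.** In simulations with no treatment effect (5,000 trials per setting, 40% risk, scores 0-4 spread 5/25/35/25/10%, odds ratio 1.5 to 2.5 per Apfel point), the chi-square rejected in 1.3 to 1.4% of trials against a nominal 1.25%. Ignoring the score does not inflate the error rate.

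**4. Gain from adjustment, tests calibrated to equal size.** Assumptions: 50 per arm, two-sided 0.0125, 40% control risk, scores spread 10/25/30/25/10%. The adjusted test is logistic regression with the score as a covariate.

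| Log-odds slope per point | Treatment odds ratio | Unadjusted power | Adjusted power | Gain (points) |
|---|---|---|---|---|
| 0.85 | 0.25 | 55.5% | 60.9% | 5.4 |
| 0.85 | 0.375 | 28.7% | 32.4% | 3.7 |
| 0.85 | 0.5 | 13.3% | 14.8% | 1.5 |
| 0.5 | 0.25 | 61.2% | 63.5% | 2.3 |
| 0.5 | 0.375 | 31.9% | 33.7% | 1.8 |
| 0.5 | 0.5 | 15.8% | 16.6% | 0.8 |
| 0.3 | 0.25 | 66.3% | 66.0% | −0.3 |

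**5. Mantel-Haenszel instead.** With strata 0-1, 2 and 3-4, type I error was 1.2 to 1.3%. The average gain was again about 0 to 5 points. With little or no gradient there was a loss of 1 to 2 points.

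**6. Chance imbalance.** Consider the tenth of trials in which the gabapentin enacarbil arm has a mean score at least about 0.3 points higher (20,000 trials per setting, score spread as in step 3, treatment odds ratio 0.25, odds ratios per point 1.5/2.0/2.5). Chi-square power falls from 65/59/53% overall to 53/38/28%, while Mantel-Haenszel holds 62/56/55%. With no treatment effect, the same imbalance produces an average difference in incidence of 3 to 7 points in those trials.

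**The case against.** The strongest reply is that nothing here is wrong. A two-tailed chi-square on randomized arms is a valid test of Aim 2. Chance imbalance is already allowed for in its type I error rate, and crude proportions speak directly to incidence, which is what the aim concerns. This stands in full. A reader might infer that the unadjusted test is biased or that its error rate is inflated. The simulated null rates in step 3 show otherwise, and the differences in step 6 are conditional on an unlucky allocation; they average out over randomization.

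A reader might also infer that the protocol collects the score in order to analyse Aim 2. The text says only that individual risk will be determined, in a list of baseline data. It ties the score to no aim or analysis, and the descriptive balance check is a plausible use.

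A larger power loss is also tempting to claim. A likelihood-ratio test from logistic regression at a treatment odds ratio of 0.25 shows 58% against 67% with slope 0.85, and 67% against 71% with slope 0.5. Those gains of 4 to 9 points rest on a very large assumed effect and on a test that is slightly liberal at this size (1.3 to 1.7% under the null in the simulations run). At equal size the gain shrinks to that in step 4.

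What survives the objection is narrower: a predictor already in hand goes unused, and the balance check may reveal an imbalance without a rule for handling it.

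**Conclusion.** The point holds as a low-severity, optional improvement to one of four secondary endpoints. The planned test is sound and the primary conclusion is untouched. With an assumed 40% control risk and a log-odds slope of 0.5 to 0.85 per Apfel point, a size-correct adjusted test adds about 0 to 5 percentage points of power; with a weak gradient it adds nothing or costs up to about 2 points. None of the scenarios simulated reaches 80% power with or without adjustment, so adjustment does not rescue the endpoint. The more useful benefit is a method fixed in advance for a chance imbalance in baseline risk. All the power figures rest on assumed event rates, score distributions and gradients, since the documents supply none of these.

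**What to change.** In section 7.2, name one analysis for 72-hour nausea and vomiting: a two-sided Mantel-Haenszel test stratified by baseline Apfel score (0-1, 2, 3-4), at the existing 0.0125 level. Report crude percentages and the risk difference beside it, and keep the unadjusted chi-square as a supporting analysis. List the Apfel score by name in the baseline comparison.

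A single named test is preferable to a choice between methods, which would leave the analysis open. Mantel-Haenszel held its size in the simulations, whereas the logistic likelihood-ratio test ran slightly high.

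The cost is a sentence or two in 7.2 and one line in the baseline table. No new data, visits or patients are needed. The statistical price is the possible loss of up to about 2 points of power if the score proves a weak predictor in this population. The change should be made before unblinding.
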